1.3 Study Therapy

1.3.1 FSRT

Fractionated stereotactic surgery (FSRT) will be administered once daily, every weekday for a total of 10 daily treatments. All subjects will receive the 30-35 Gy in 10 daily fractions, as determined by the treating physician. Radiation treatment interruptions for up to 3 days are permitted for any reason. Interruptions of 4 to 7 treatment days will be considered an acceptable protocol violation. For interruptions of 8 days or greater, an unacceptable deviation will be assigned.

All patients will have CT simulation and high resolution MRI with contrast for radiation treatment planning. The gross tumor volume (GTV) will be defined by the contrast-enhanced T1 abnormality on the post-operative MRI scan. This will generally include the surgical cavity margins from the most recent surgical procedure as well. There is no clinical target volume (CTV) or planned target volume (PTV) expansion.

All patients will receive 35 Gy in 3.5 Gy fractions. This dose may be reduced to 30 Gy in 10 fractions per the treating physician if the GTV is large (> 50 cc) or close to critical structures (such as brainstem, optic nerves, or chiasm). The dose is prescribed to the highest isodose line that covers >99% of the GTV.

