6.2 Definition of Dose-Limiting Toxicities

Dose-limiting toxicities (DLTs) will be graded in severity according to the guidelines outlined in the NCI-CTCAE version 4.0. Dose-limiting hematologic and non-hematologic toxicities will be defined differently, and will be based on events that occur during study drug administration and for 30 days after the completion of the radiation therapy. In order to be declared a dose-limiting toxicity, an adverse experience must be related (definitely, probably, or possibly) to study therapy.

If a patient experiences a DLT during the radiation phase or the 30 day post radiation observation period, the patient will be permanently discontinued from study.

A dose-limiting toxicity (DLT) will be defined as follows:

- All grade 3 or higher toxicities that occur during or within 30 days of completing radiation treatment will be considered “treatment related” with the exception of (1) symptoms that are clearly related to the cancer or other pathology (in the opinion of the treating physician), and (2) expected sequelae of the neurosurgical procedure or radiosurgery. All neurological symptoms will be considered “treatment related” unless they are present at study onset, expected sequelae of the neurosurgical procedure, or clearly related to disease progression.
- Febrile neutropenia (even in the absence of hospitalization)
- Hematologic DLTs will be defined as either Grade 4 neutropenia lasting for ≥ 7 days in duration, any Grade 4 anemia, any Grade 4 thrombocytopenia, or any Grade 5 hematologic toxicity. All patients will be evaluated for hematologic toxicity.
- Any neurological toxicity of Grade 3, 4 or 5 will be considered a DLT, with the exception of 1) symptoms present prior to study enrollment, and 2) expected sequelae of the neurosurgical procedure.
- Grade 3 event of hypocalcemia, hypophosphatemia, hypokalemia, or hypomagnesemia lasting more than 24 hours without responding to medical therapy; or responding to medical therapy and lasting more than 72 hours
- Grade 3 transaminases elevation associated with \geq grade 2 bilirubin elevation (Hy’s law)

will also be a DLT defining event.

- Non-hematologic dose-limiting toxicity will be defined as any Grade 3, 4 or 5 non-hematologic toxicity, with the specific exception of:
 - Grade 3 nausea or Grade 3 vomiting that in the opinion of the Investigator occurs in the setting of inadequate compliance with supportive care measures and lasts for less than 48 hours.

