 - Grade 3 diarrhea that in the opinion of the Investigator occurs in the setting of inadequate compliance with supportive care measures and lasts for less than 48 hours.
 - Grade 3 dehydration that, in the opinion of the Investigator occurs in the setting of inadequate compliance with supportive care measures and lasts for less than 48 hours.
 - Grade 3 acidosis or alkalosis which responds to medical intervention by returning to \leq Grade 2 within 48 hours.
 - Isolated Grade 3 elevation of liver function tests (LFTs) without associated clinical symptoms, lasting for \leq 14 days in duration.
 - Grade 3 hypocalcemia, hypokalemia, hypomagnesemia, hyponatremia, or hypophosphatemia which responds to medical intervention.
 - Grade 3 hypercholesterolemia.
 - Grade 3 hypertriglyceridemia.
 - Grade 3 alopecia

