6.3 Dose escalation/de-escalation

Dose escalation will proceed within each cohort according to a “3+3 design”, as explained in the following scheme. Dose-limiting toxicity (DLT) is defined above. The toxicity assessment period is 30 days after the completion of the radiation therapy.

Dose Level	Alisertib dose
-1	10 mg BID
1	20 mg BID
2	30 mg BID
3	40 mg BID
4	50 mg BID (final dose level)

Number of Patients with DLT at a Given Dose Level[†]	Escalation Decision Rule
0 out of 3	Enter 3 patients at the next dose level.
≥ 2	Dose escalation will be stopped. This dose level will be declared the maximally administered dose (highest dose administered). Three (3) additional patients will be entered at the next lowest dose level if only 3 patients were treated previously at that dose.
1 out of 3	Enter at least 3 more patients at this dose level. 
 • If 0 of these 3 patients experience DLT, proceed to the next dose level.

	
 If 1 or more of this group suffer DLT, then dose escalation is stopped, and this dose is declared the maximally administered dose. Three (3) additional patients will be entered at the next lowest dose level if only 3 patients were treated previously at that dose.
≤1 out of 6 at highest dose level below the maximally administered dose	This is generally the recommended phase 2 dose. At least 6 patients must be entered at the recommended phase 2 dose.
†Dose escalation will be determined based on the occurrence of DLTs. For the purposes of determining whether to advance the Dose Level, DLTs will be counted by patient (i.e., a patient who experiences more than 1 DLT will be counted only once).	

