7.2 Statistical Methods

We will use a two-stage accrual design at each dose considered. We will initially enter 3 subjects at each dose. If none of the three experiences a dose-limiting toxicity we will proceed to the next dose. If one of the three experiences that level of toxicity, we will accrue 3 more subjects at that dose. If at any time there are two or more dose-limiting toxicities (in the 3-6 subjects) on a given dose, we will terminate accrual to the Phase I portion of that trial. No patient will be treated at a higher dose until the 3 or 6 patients have completed their toxicity evaluation period at the current dose. With this plan, a dose with a 50% or greater probability of causing a dose-limiting toxicity has at most a 12.5% chance of satisfying the conditions for dose escalation after the first 3 subjects and at least a 50% chance of stopping at 3. With the two-stages (3-6) together, there is at most a 17.2% chance of satisfying the conditions for dose escalation after the 6 subjects.

The maximally tolerated dose (MTD) will then be the last dose studied or the previous dose, based on Investigator's clinical judgment of the degree of toxicity seen at the last dose. While waiting for the 3 or 6 subjects accrued according to plan to complete their toxicity evaluation period, up to 3 additional subjects may be accrued at the current dose. These additional subjects will not count towards the formal plan of stopping at two or more toxicity occurrences, but will contribute to the judgment as to the MTD.

We will also conduct some descriptive analyses that will help in the design of a possible phase-II trial. Among patients at the MTD in each arm, we will estimate the proportion with complete or partial response, as well as the median survival (through the Kaplan-Meier method). We will also compute associated 95% confidence intervals, although we realize that they will be very wide (given that we only anticipate 6-8 patients to be treated at the MTD in each arm). The estimates themselves, however, will help in the sample size calculations of possible future phase-II trials.

Progression free survival and overall survival will be measured from the date of starting study treatment (first day of radiation treatment). Progression free survival will be assessed by the treating physician based on the brain MRI.

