Appendix II: Visit Schedule

	Prior to Registration	Pre-treatment	Concurrent phase		Observation phase	Maintenance phase	Recommended Follow up
Time (day)	-14 to -1	-30 to -1	1-7	8-14	Day 13-42	From Day 43 to 1 year	Year 2 and onwards
Informed consent	X						
Demographics	X						
Medical history	X	X					
H & P	X	X	X ⁷	X ⁷	X ⁵	Q 2 months	X ⁶
Neuro exam	X	X	X ⁸	X ⁷	X ⁵	Q 2 months	X ⁶
MMSE		X			X ⁵	Q 2 months	X ⁶
QoL		X			X ⁵	Q 2 months	X ⁶
Vitals		X	X ⁷	X ⁷	X ⁵	Q 2 months	X ⁶
Weight		X	X ⁷	X ⁷	X ⁵	Q 2 months	X ⁶
KP/ECOG	X	X	X	X ⁷	X ⁵	Q 2 months	X ⁶
CBC w diff	X	X	X ⁷	X ⁷	X ⁵	Weekly ³	X ⁶
CMP, Mg +	X	X	X ⁸	X ⁷	X ⁵	Q 2 months	X ⁶
PT/PTT/INR		X					
Lipid Panel			X ⁷	X ⁷	X ⁵	Q 2 months	
EKG		X					
b-HCG	X ⁹						
MRI Brain		X			X ¹	Q 2 months	X ⁶
Treatment:							
RT			X ²	X ²			
MLN8237			X ³	X ³		X ⁴	

Q = every

H & P = History & Physical

NOTE:

1. Brain MRI should be done between days 35-42, then every 2 months for 1st year.
2. RT: daily on weekdays for a total of 10 treatments.
3. Alisertib: BID on days of RT only.
4. Alisertib: 50 mg BID on days 1-7 every 21 days, for up to 18 cycles or until progression.
5. Between day 39 to day 45 (at the end of 30 day observation period), then every 2 months
6. Every 3 months from year 1 to year 2, then every 4-6 months afterwards.
7. All items only need to be done at least once during week 1 and at least once during week 2.
8. Until discontinuation of Alisertib.
9. Pregnancy test should be done within 7 days prior to registration, if applicable

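### The one scheduled post-radiation assessment (days 39–45 from start) does not track the 30-day DLT window, and nothing makes escalation wait for it or for a pending Grade 4 neutropenia

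*Combined protocol and SAP*

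**What the plan says.** Section 7.2 sets the condition for moving up: "No patient will be treated at a higher dose until the 3 or 6 patients have completed their toxicity evaluation period". Section 6.3 gives the length of that period: "The toxicity assessment period is 30 days after the completion of the radiation therapy". Section 6.2 bases DLTs on the same span: "based on events that occur during study drug administration and for 30 days after the completion of the radiation therapy". The period is thus measured from the last fraction, and none of these sections mentions a visit or a result.

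Appendix II counts from treatment start instead. It shows the observation phase as days 13 to 42 and maintenance from day 43. The physical examination, neurological examination, CBC and chemistry each appear once in the observation column, timed by note 5: "Between day 39 to day 45 (at the end of 30 day observation period), then every 2 months". The brain MRI has its own range, days 35–42. The previous examination and blood tests are due once in week 2 (days 8–14). Note 2 gives the radiation schedule as "RT: daily on weekdays for a total of 10 treatments", and section 1.3.1 adds: "Radiation treatment interruptions for up to 3 days are permitted for any reason".

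Several DLT criteria in section 6.2 depend on duration. The two longest are:

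- Grade 4 neutropenia, which is a DLT only at 7 days or more.
- "Isolated Grade 3 elevation of liver function tests (LFTs) without associated clinical symptoms", which is exempt from the general Grade 3–5 rule if it lasts no more than 14 days.

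Section 10.1 requires the medical monitor to review adverse events and safety data observed at each new dose level before escalation.

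**The concern.** A 3+3 decision needs the DLT status of every patient in the cohort. A team that follows sections 6.3 and 7.2 and Appendix II to the letter could open the next dose in any of three situations:

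- the last patient's end-of-window examination and blood tests have not yet been done;
- that assessment was done days before the window closed, with no other clinical or laboratory assessment scheduled in the observation phase;
- a Grade 4 neutropenia is known but has not yet run 7 days.

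If such a patient is tallied as free of DLT, the error can only favour escalation. The next cohort would then be exposed before the safety check on the current one is complete. The operating characteristics in section 7.2 also presume that every DLT is classified when the decision is made.

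**Working it through.** **1. The plan's own figures.** With a true DLT probability of 0.5:

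- P(0 of 3) = 0.5³ = 0.125.
- P(2 or more of 3) = 0.500.
- P(escalate, both stages) = 0.125 + 0.375 × 0.125 = 0.171875.

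These match the stated 12.5%, 50% and 17.2%. The figures are correct, given complete classification.

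**2. When the 30 days end.** Ten weekday fractions are counted from day 1, and closure is the last fraction plus 30. The permitted 3 days of interruption are read as treatment days, the unit that section 1.3.1 uses in its next sentence.

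| Course | Last fraction | Window closes | Day 39 visit | Day 45 visit |
|---|---|---|---|---|
| Monday start, uninterrupted | day 12 | day 42 | 3 days before | 3 days after |
| Tuesday–Friday start, uninterrupted | day 14 | day 44 | 5 days before | 1 day after |
| 3 treatment days missed, Monday–Wednesday start | day 17 | day 47 | 8 days before | 2 days before |
| 3 treatment days missed, Thursday–Friday start | day 19 | day 49 | 10 days before | 4 days before |

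The calendar's days 13–42 fit only the first row.

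**3. Share of the seven permitted visit days (39–45).**

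- After closure: days 43, 44 and 45 for a Monday start, 3/7 = 43%. Day 45 only for a Tuesday–Friday start, 1/7 = 14%. None with 3 missed days.
- At or after closure: days 42–45, 4/7, for a Monday start. Days 44–45, 2/7, for a Tuesday–Friday start. 0/7 with 3 missed days.

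Treating these shares as probabilities assumes that visits are spread evenly over the range. They apply to the patient whose completion gates the decision.

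**4. Pending Grade 4 neutropenia.** The gap since the week-2 check is 39 − 14 = 25 to 45 − 8 = 37 days, so onset may well be unknown. Counting 7 days from first detection gives day 39 + 7 = 46 to day 45 + 7 = 52. All of these are later than day 42 or 44. With closure on day 47 or 49, only a case found early enough (by day 40 or day 42 respectively) could be settled by closure. Sections 6.2, 6.3 and 7.2 do not say how an unsettled case is counted.

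**5. Isolated Grade 3 LFT elevation.** Section 6.2 makes any Grade 3–5 non-hematologic toxicity a DLT and then lists exceptions. An elevation whose duration is unknown has not yet met the 14-day exception, so it is a DLT by default. Dated from detection on days 39–45, it passes 14 days only after days 53–59 (39 + 14, 45 + 14). From day 43 chemistry is due only every 2 months, so no scheduled test would show that the exception applies.

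**6. Direction of error (illustration only).** The documents do not say what fraction q of DLTs might be unclassified at the decision, so q is assumed. Suppose that only the last patient in each group of 3 is affected and that an unclassified patient is counted as DLT-free. At a true rate of 0.5, that patient shows a DLT with probability 0.5(1 − q). For q = 0.2 this is 0.4:

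- P(0 of 3) = 0.25 × 0.6 = 0.15.
- P(1 of 3) = 0.5 × 0.6 + 0.25 × 0.4 = 0.40.
- P(escalate) = 0.15 + 0.40 × 0.15 = 0.21.

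The same steps give 19.1% at q = 0.1 and 23.0% at q = 0.3, against 17.2% at q = 0.

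**The case against.** The case on the other side is substantial:

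- Section 7.2 states a minimum condition. It does not order automatic release on a given day.
- Note 5 describes its visit as falling at the end of the observation period. Completing the toxicity evaluation can fairly be read to include that visit.
- The medical monitor reviews the data before each escalation.
- CBC is weekly from day 43, and section 6.4 asks for at least twice-weekly counts for a known neutropenia, though among the dose-modification rules.
- The 7 days run from onset, so the neutropenia problem arises only when onset is unknown or close to the visit.

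These points narrow the concern without removing it. The favourable reading of note 5 closes the gap of up to 3 days, but it does not help when the whole visit range precedes closure, and it does not settle a pending neutropenia. The monitor's review covers what has been observed. It requires neither this visit nor a final DLT status.

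Four stronger readings are tempting, and the documents do not support them:

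- **An abnormality found on days 43–45 cannot be a DLT.** Section 6.2 counts events by when they occur, so late detection does not exclude an earlier onset.
- **A pending LFT elevation counts as no DLT.** The default in section 6.2 runs the other way.
- **The 3/7 or 1/7 share can be compounded over 3 or 6 patients to give the risk per cohort.** With staggered entry, earlier patients' visits will generally be done when the last patient finishes, so mainly the last patient matters.
- **The 12.5%, 50% and 17.2% are wrong.** They reproduce exactly.

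**Conclusion.** The point holds as an inconsistency between a DLT window counted from the last fraction and an assessment range counted from day 1, together with a missing rule for pending events. The scheduled assessment may fall up to 3 days after closure (Monday start) or 1 day after (Tuesday–Friday start). With 3 missed treatment days it falls 2 to 10 days before closure. No section makes escalation wait for an assessment that covers the window.

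On the even-spread assumption, 43% or 14% of visits by the gating patient in an uninterrupted course fall after closure. That is neither the chance that a cohort opens in the gap nor the chance that a DLT is missed; the documents give no basis for estimating either. A Grade 4 neutropenia first seen at the visit with unknown onset stays unsettled until about days 46–52. The LFT criterion needs only a clarifying word.

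This should be corrected. Careful conduct could avoid the problem, but the text as written does not require it.

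**What to change.** Reconcile sections 6.2, 6.3 and 7.2 with Appendix II:

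- **(a)** Anchor the note 5 visit to the last radiation fraction, not to day 1.
- **(b)** State in sections 6.3 and 7.2 that a patient counts as evaluated for escalation only when an assessment at or after 30 days post-radiation is done and its results are available.
- **(c)** State that an event with onset in the window whose DLT status depends on duration is not counted as a non-DLT until it is classified. Add that an isolated Grade 3 LFT elevation stays a DLT until the exception is shown to apply.
- **(d)** Assign events to the DLT window by onset date, not automatically because they were found at this visit. Reconcile the visit range with the day 43 start of maintenance. A visit on days 43–45 may follow the first maintenance doses, and charging every finding there to the cohort dose could misattribute a maintenance effect. The Study Summary times maintenance from the end of radiation while Appendix II uses day 43, so those two also need to agree.

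This is more than a change of wording: step (b) removes the permitted visit days that precede closure. The next cohort may open a few days later, or longer while a duration-dependent event is pending, and an abnormal result may need repeat tests. Section 7.2 already allows up to 3 more subjects at the current dose while a cohort's evaluation is awaited, so accrual need not stop.

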--	---

Study Therapy, Dose, Route, Regimen	Alisertib (MLN8237) will be administered by mouth, twice daily. The dose of Alisertib will be defined by the protocol.
Duration of administration and follow-up	Concurrent with radiation treatment, then 30 days after finishing radiation therapy will receive twice daily from day 1-7, every 21 day cycle for up to 18 cycles, or until tumor progression.
Reference therapy	None. This is a phase I study
Statistical Methodology	We will use a two-stage accrual design at each dose considered. We will initially enter 3 subjects at each dose. If none of the three experiences a dose-limiting toxicity we will proceed to the next dose. If one of the three experiences toxicity at that level, we will accrue 3 more subjects at that dose. If at any time there are two or more dose-limiting toxicities (in the 3-6 subjects) on a given dose, we will terminate accrual to the Phase I portion of that trial. No patient will be treated at a higher dose until the 3 or 6 patients have completed their toxicity evaluation period at the current dose. With this plan, a dose with a 50% or greater probability of causing a dose-limiting toxicity has at most a 12.5% chance of satisfying the conditions for dose escalation after the first 3 subjects and at least a 50% chance of stopping at 3. With the two-stages (3-6) together, there is at most a 17.2% chance of escalation.

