Schema	 
The flowchart illustrates the study schema. It begins with a box: "FSRT (35 Gy in 3.5 Gy fractions)+ MLN8237 20 mg BID on days of RT". This leads to a decision diamond "DLT?". If "Yes", it leads to "FSRT (35 Gy in 3.5 Gy fractions)+ MLN8237 10 mg BID on days of RT". If "No", it leads to "FSRT (35 Gy in 3.5 Gy fractions)+ MLN8237 30 mg BID on days of RT". This second step also leads to a "DLT?" diamond. If "Yes", it leads to "No further escalation". If "No", it leads to "FSRT (35 Gy in 3.5 Gy fractions)+ MLN8237 40 mg BID on days of RT". This third step leads to a "DLT?" diamond. If "Yes", it leads to "No further escalation". If "No", it leads to "FSRT (35 Gy in 3.5 Gy fractions)+ MLN8237 50 mg BID on days of RT", which is labeled as the "Final dose level". A large blue arrow labeled "30 days Since finishing FSRT (no treatment)" points from the final dose level box to a yellow box on the right labeled "Maintenance Treatment". The maintenance treatment box contains the text: "MLN8237 50 mg BID on days of RT every 21-day cycle up to 18 cycles, or until tumor progression".

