6.0 STUDY PROCEDURES

6.1 Study Visit Schedule

Please see *Appendix II* for study calendar.

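### Appendix II fixes the observation phase and maintenance start by study day, but the DLT window runs from the last radiation fraction; they agree only after an uninterrupted Monday start

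*Combined protocol and SAP*

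**What the plan says.** Section 6.1 sends the site to the appendix for timing: "Please see *Appendix II* for study calendar". Appendix II then works in study days. Observation is days 13 to 42, and the maintenance column is headed "From Day 43 to 1 year". Footnote 5 times the observation-phase history and physical, neurological examination, blood count and chemistry: "Between day 39 to day 45 (at the end of 30 day observation period), then every 2 months". The MRI has its own range, days 35 to 42.

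The rest of the protocol counts from the end of radiation:

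- Study Summary, duration of administration: after the concurrent phase, patients "then 30 days after finishing radiation therapy will receive twice daily from day 1-7" of each 21-day cycle.
- Schema: the gap before maintenance is labelled "30 days Since finishing FSRT (no treatment").
- Section 6.2: "All grade 3 or higher toxicities that occur during or within 30 days of completing radiation treatment will be considered" treatment related, with listed exceptions.
- Section 6.3: "The toxicity assessment period is 30 days after the completion of the radiation therapy".
- Section 6.4: a DLT during radiation or in the 30-day post-radiation observation period takes the patient off study permanently.

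Section 1.3.1 gives ten fractions, one per weekday, and allows slippage: "Radiation treatment interruptions for up to 3 days are permitted for any reason". No start weekday is fixed, and nothing tells the site to move the Appendix II days when the last fraction moves.

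**The concern.** The DLT count decides escalation, so the days on which an event counts should be unambiguous. Two timing rules that coincide for only one start day leave a site with conflicting instructions even when it complies fully with Section 1.3.1.

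Two things could follow.

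- A site that starts maintenance on day 43 may give 50 mg twice daily while the DLT window is still open. That dose is the same for every cohort, so at dose level 1 (20 mg) it is 50/20 = 2.5 times the dose being evaluated; at level 4 it is equal. A toxicity caused by maintenance could then be charged to the cohort dose, and the patient removed under Section 6.4. That error would push toward a lower MTD.
- A footnote 5 visit held before the window closes could miss a late laboratory DLT, which errs the other way.

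**Working it through.** **Inputs.** Ten fractions, one per weekday (Section 1.3.1; Appendix II, footnote 2). Up to three days of interruption permitted (Section 1.3.1). DLT window closing 30 days after the last fraction (Sections 6.2, 6.3). Calendar days 13 to 42, 43, and 39 to 45 (Appendix II).

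**Assumptions.** Day 1 is the first fraction; Appendix II does not define it, but Section 7.2 measures survival from the first radiation day. Interruption days are counted as missed treatment days, the unit Section 1.3.1 uses for longer interruptions. Missed fractions are made up on later weekdays.

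**Formulas.** With k missed fractions, L is the (10 + k)th weekday counted from day 1.

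- Observation: L+1 to L+30.
- First day after the window: L+31.
- Overlap of a literal day 43 start with the window: days 43 to L+30, which is L − 12 days.
- Footnote 5 days at or after the window end: those of days 39 to 45 that are L+30 or later.

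**Reproducing the plan.** For a Monday start with k = 0, weekdays fall on days 1–5 and 8–12, so L = 12. Observation is days 13 to 42 and the next day is 43, exactly as in Appendix II. This also shows that the appendix was built on the L+31 convention.

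**Other start days.** For an uninterrupted Tuesday start, weekdays fall on days 1–4, 7–11 and 14, so L = 14. Wednesday, Thursday and Friday starts also give L = 14, because each crosses two weekends.

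| Missed fractions | Start day | L | Window ends (L+30) | Overlap of day 43 start | Footnote 5 days at or after window end |
|---|---|---|---|---|---|
| 0 | Mon | 12 | 42 | 0 | 4 of 7 (42–45) |
| 0 | Tue–Fri | 14 | 44 | 2 | 2 of 7 (44–45) |
| 1 | any | 15 | 45 | 3 | 1 of 7 (45) |
| 2 | Mon–Thu | 16 | 46 | 4 | 0 of 7 |
| 2 | Fri | 18 | 48 | 6 | 0 of 7 |
| 3 | Mon–Wed | 17 | 47 | 5 | 0 of 7 |
| 3 | Thu–Fri | 19 | 49 | 7 | 0 of 7 |

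The observation phase and maintenance start match the body text in the first row only. The visit range is more tolerant: it contains the window end in the first three rows and misses it in the other four.

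**The case against.** The strongest reply is that the body text already governs. The Study Summary starts maintenance 30 days after radiation ends, and the schema calls that gap treatment-free. To dose early, a site would have to prefer a column header to explicit instructions. The headers also look nominal: the concurrent phase runs to day 14 while observation starts on day 13, and 18 cycles from day 43 would dose until day 43 + 17 × 21 + 6 = 406, past one year. The day 43 header can be read as an earliest date. This stands, and it is why the overlap arises only on a literal reading.

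Footnote 5 can likewise be read by its stated purpose. Its parenthetical puts the visit at the end of the observation period, which Section 6.4 ties to radiation, so the visit would move with L and no shortfall would arise. A reader might infer that the visit falls short on any reading; the parenthetical does not support that. What remains is that with two or more missed fractions the printed days contradict the parenthetical beside them.

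The printed range also accepts a visit on day 39 for a window ending on day 42, three days early. With the same tolerance, a day 45 visit serves a window ending by day 48, leaving only three missed fractions with a Thursday or Friday start (day 49) outside, by one day. This shows the shortfall is small; it does not remove the contradiction.

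A reader might also infer that nothing is scheduled after the window closes. That is not so: Appendix II has weekly blood counts and two-monthly examinations during maintenance. But those belong to the maintenance phase, which should not begin until the DLT assessment is done.

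Other safeguards stand. Adverse events are sought at every contact (Section 8.2). Escalation waits for completed toxicity evaluation (Section 7.2) and medical-monitor review (Section 10.1). The institution's 147-patient series, without alisertib, reported no radiation interruptions (Section 1.2.2), which makes the 0- and 2-day rows the likeliest.

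**Conclusion.** Appendix II is wrong as written: an internal inconsistency in a dosing and assessment calendar. Severity is minor.

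Its observation phase and maintenance start agree with the end-of-radiation definitions only for an uninterrupted Monday start. Otherwise a literal day 43 start falls 2 days inside the DLT window (uninterrupted Tuesday to Friday start), 3 days (one missed fraction) or 4 to 7 days (two or three). The Monday-only statement does not extend to the visit range, which includes the window end with no or one missed fraction. With two or more, its literal days all precede that end. These figures rest on day 1 being the first fraction and on missed fractions being made up on weekdays.

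A reader might go further and infer that patients will be dosed inside the window or that the MTD will be biased. The documents do not support that, because the body text carries the correct anchor. No sample size or escalation rule is affected.

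**What to change.** Restate Appendix II relative to L, the last radiation fraction:

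- observation phase: L+1 to L+30;
- footnote 5 visit and laboratory tests: at the end of that period, about L+30, and before maintenance;
- first maintenance dose: no earlier than L+31, and only after the DLT assessment is complete.

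For an uninterrupted Monday start the phase days are unchanged. The cost is calendar wording in an amendment, with no added visits or patients. Compared with a literal day 43, the earliest first maintenance dose moves by L − 12 days: 0 (uninterrupted Monday), 2 (uninterrupted Tuesday to Friday), 3 (one missed fraction), 4 or 6 (two) and 5 or 7 (three).
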